9.4. Transepidermal water loss (TEWL)

TEWL (as measured by a tewameter) readings were taken on Day 0, 2, 4, 6, 8 and 10. At each time point two readings were taken. The average of the two readings will be determined and used for the analysis described below.

TEWL and change in TEWL will be summarised by day, presenting the number of subjects, mean (with standard deviation) and median, minimum and maximum for each treatment group. Change from baseline (mean and 95% CI) in TEWL will also be plotted over time. Day will be presented on the x-axis and the change from baseline will be presented on the y-axis.

Change in TEWL will also be analysed using a MMRM following the methods specified in Section 9.1.

Following the interim analysis, investigation will also be conducted into the effect of age category on TEWL. A similar approach to that of the weight endpoint will be considered for the statistical analysis except all subjects will be included in the analysis rather than only subjects without oedema.

9.5. Skin redness

Skin redness (as assessed by the colorimeter) readings for L, a and b were taken on Day 0, 2, 4, 6, 8 and 10. At each timepoint two readings of L, a and b were taken. The average

of the two readings will be determined and used for the analysis described below. L, a and b will be summarised separately.

Skin redness and change in skin redness will be summarised by day, presenting the number of subjects, mean (with standard deviation) and median, minimum and maximum for each treatment group. Change from baseline (mean and 95% CI) in skin redness will also be plotted over time. Day will be presented on the x-axis and the change from baseline will be presented on the y-axis.

Change in skin redness will also be analysed using a MMRM following the methods specified in Section 9.1.

Following the interim analysis, investigation will also be conducted into the effect of age category on skin redness. A similar approach to that of the weight endpoint will be considered for the statistical analysis except all subjects will be included in the analysis rather than only subjects without oedema.

9.6. Skin Appearance Score

Derivations

Skin appearance score is collected on Days 0, 2, 4, 6, 8 and 10. The total score will be summarised as described below, the individual components which make up the total score will not be summarised.

Summary Statistics

The absolute and change from baseline values for skin appearance score will be summarised by day, presenting the number of subjects, mean (with standard deviation) and median, minimum and maximum for each treatment group. The summaries will also present summary statistics of the endpoint on the last day the subject was in the study.

Change from baseline (mean and 95% CI) for skin appearance score will also be plotted over time. Day will be presented on the x-axis and the change from baseline will be presented on the y-axis. The mean at each day will be presented with an associated 95% CI.

Mixed model repeated measures analysis

Change from baseline in skin appearance score will be analysed using a MMRM following the methods specified in Section 9.1.

Following the interim analysis, investigation will also be conducted into the effect of age category on skin appearance score. A similar approach to that of the weight endpoint will be considered for the statistical analysis except all subjects will be included in the analysis rather than only subjects without oedema.

Further analysis

Non-linear modelling and latent growth curves may be considered if deemed appropriate.

9.7. SCORDoK Score

Skin condition as measured by the modified SCORDoK score is collected on Days 0, 2, 4, 6, 8 and 10.

SCORDoK scores will be provided by icddr,b, GSK and the Denmark SCORDoK team but only scores from iccdr,b will be included in the outputs specified in this RAP.

A summary table showing the number and percent of subjects with each type of skin manifestation will be produced by day and treatment group. The table will also show the grade for ichtyosiform skin changes, lichenoid skin changes and bullae-erosions-desquamations.

Further analysis of the SCORDoK score may be carried out by the Denmark SCORDoK team but this work is out of score for this RAP.

Following the interim analysis, SCORDoK will also be summarised by age category.

9.8. Plasma Fatty Acids

Fatty acid (FA) data will not be included in the interim analysis as the results will not be available until the end of the study. The fatty acid data will be analysed as part of the final analysis.

Fatty acids at Day 0 and Day 10 will be summarised along with the change in FA and percentage change in FA at Day 10. The data displays and exploratory analysis of the FA data will be performed by Metabolon Inc, and further analyses may be performed by the

Statistics group of the GSK subsidiary Cellzome. GSK Statistics and Programming team will assist in these analyses as needed including providing any datasets or covariates for statistical analyses.

9.9. Plasma C-Reactive Protein (CRP)

CRP at Day 0 and Day 10 will be summarised along with the change in CRP and percentage change in CRP at Day 10. The output will present the number of subjects, mean (with standard deviation) and median, minimum and maximum for each treatment group.

The number and percentage of subjects with positive and negative CRP levels will also be summarised, where positive is a CRP value > 0.5 mg/dL and negative is a CRP value ≤ 0.5 mg/dL.

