7. DERIVED DATA

7.1. Baseline

For assessments that were collected on the daily monitoring chart, baseline is considered to be the subjects Day 1 assessment as collected on the CRF. For all other assessments, baseline is considered to be the subject's Day 0 assessment as collected on the CRF. If there are multiple assessments on Day 0 (or Day 1 for assessments from the daily monitoring chart) then the earliest will be taken as the baseline.

Change from baseline for post-baseline records will be calculated by subtracting the baseline value from the post-baseline value. If either the baseline or post-randomisation value is missing, the change from baseline is set to missing.

Percentage Change from Baseline will be calculated as

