9.10. Pro-inflammatory cytokines

Pro-inflammatory cytokines (including IL-1ß, IL-2, IL-4, IL-5, IL-6, IL-7, IL-8, IL-10, IL-12p70, IL-13, IL-17, TNF- $\dot{\alpha}$, G-CSF, GM-CSF, IFN- γ , MCP-1 (MCAF) and MIP-1 β) will be summarised at Day 0 and 10 along with the change in pro-inflammatory cytokines and percentage change in pro-inflammatory cytokines at Day 10. The output will present the number of subjects, mean (with standard deviation) and median, minimum and maximum for each treatment group.

For laboratory values that are above or below the lower limit of quantification or out of range (OOR), that have character values starting with "<" or ">," numeric values will be derived using the following rules, where, for example, IL5I is the character result in standard units, and IL5 is the numeric version of the result:

if IL5I > x then IL5 = x + 1, where x is an integer ≥ 1 . if IL5I > x.y then IL5 = x.y + 0.1, where x, y are integers. if IL5I > x.yz then IL5 = x.yz + 0.01, where x, y, z are integers etc.

if IL5I "< x" then IL5 = x - 1, where x is an integer >= 1. if IL5I "< x.y" then IL5 = x.y - 0.1, where x, y are integers. if IL5I "< x.yz" then IL5 = x.yz - 0.01, where x, y, z are integers etc.

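### For CRP and cytokines, the arithmetic mean (SD) of percentage change is pulled upward by spread alone, and the cytokine below-limit rule can leave percentage change undefined

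*SAP*

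**What the plan says.** **CRP (SAP 9.9).** Day 0 and Day 10 values are "summarised along with the change in CRP and percentage change in CRP at Day 10". The statistics are then fixed: "The output will present the number of subjects, mean (with standard deviation) and median, minimum and maximum for each treatment group". There is also a count at a cut-off of 0.5 mg/dL: "The number and percentage of subjects with positive and negative CRP levels will also be summarised".

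**Cytokines (SAP 9.10).** The same layout and statistics apply to 17 named analytes, including "percentage change in pro-inflammatory cytokines at Day 10". Out-of-range results are turned into numbers by moving one unit of the last reported digit beyond the limit: down for a '<' result, up for a '>' result.

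**Definition (SAP 7.1).** The formula is introduced by "Percentage Change from Baseline will be calculated as". The formula itself is not legible in the text available, so the usual one is assumed below.

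**Elsewhere.** Section 1.2 lists change from baseline at Day 10 in CRP and in the cytokines as secondary endpoints. Table 1 in section 6.1 assigns neither a model, and neither 9.9 nor 9.10 mentions a log scale, ratio or geometric mean. Section 6 deems all analyses exploratory.

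**The concern.** Percentage change is lopsided. A child whose CRP doubles scores +100% and a child whose CRP halves scores -50%. The two moves are equal and opposite on the ratio scale, yet they average +25%. For markers that move several-fold within a child, the arithmetic mean therefore sits above zero when the typical child is unchanged, and the excess depends on how variable the children are. Two arms with the same typical change but different spread will show different means.

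The mean (SD) is the first summary in each table. A positive value invites the reading that inflammation has worsened, and a gap between arms invites the reading that the emollient has done something. Either can come from spread alone, or from a few children with very low Day 0 values. No modelled result is planned for these endpoints to set beside that row.

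The below-limit rule adds a second difficulty for cytokines: it can put a zero in the denominator.

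**Working it through.** The plan states no figure on this point, so there is nothing to reproduce.

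**Inputs**
- Percentage change = 100 × (Day 10 - Day 0) / Day 0 (assumed).
- Within-child spread: s, the SD of log(Day 10/Day 0) on the natural-log scale. The SAP does not give it; a range of 0.2 to 1.5 is shown.
- No typical change: log(Day 10/Day 0) is normal with mean 0 (assumed). The median and geometric mean percentage change are then 0 at every s.
- 50 children per arm in the simulation (assumed).

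**Step 1: mean and SD when the typical child does not change**

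Mean = 100 × (exp(s²/2) - 1). SD = 100 × sqrt((exp(s²) - 1) × exp(s²)).

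| s | Mean % change | SD (points) |
|---|---|---|
| 0.2 | +2.0 | 20.6 |
| 0.3 | +4.6 | 32.1 |
| 0.5 | +13.3 | 60.4 |
| 0.7 | +27.8 | 101.6 |
| 0.8 | +37.7 | 130.4 |
| 1.0 | +64.9 | 216.1 |
| 1.2 | +105.4 | 368.7 |
| 1.5 | +208.0 | 897.4 |

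**Step 2: arms that differ only in spread**
- s = 0.5 v 0.8: 37.7 - 13.3 = 24 points.
- s = 0.8 v 1.2: 105.4 - 37.7 = 68 points.

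**Step 3: a true typical fall of 20%**

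Mean = 100 × (0.8 × exp(s²/2) - 1), which gives -9.3% at s = 0.5, +10.2% at 0.8 and +31.9% at 1.0. The sign turns at s = sqrt(-2 × ln 0.8) = 0.67.

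**Step 4: simulation under no typical change** (20,000 runs of one arm of 50)
- The arm's mean percentage change was positive in 75% of runs at s = 0.2, 95% at 0.5, 99% at 0.8 and over 99% at 1.0.
- For s from 0.2 to 1.2, the typical median and the typical geometric mean percentage change were within 0.2 points of 0, and the mean absolute change was about 0.

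**Step 5: the below-limit rule in 9.10**
- '<1' becomes 1 - 1 = 0; '<0.1' becomes 0.1 - 0.1 = 0; '<0.01' becomes 0.01 - 0.01 = 0.
- '<2' becomes 1 and '<0.5' becomes 0.4, so other limits keep a positive value.

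A Day 0 value of 0 makes percentage change undefined. The plan does not say whether such a child is left out of that row. The SAP does not list the assay limits, so the number of analytes affected is unknown.

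**The case against.** The strongest reply is that the same table already carries the safeguard. It shows the median, minimum and maximum, the Day 0 and Day 10 values and the absolute change, and CRP also has its positive/negative count. Absolute change is the quantity that section 1.2 names as the endpoint. A reader who sees a large mean, a median near zero and a huge maximum will recognise skewness. This largely stands, and it is why the point is minor. It does not make the mean (SD) row useful: no interval is planned for the median, and the SD beside the mean is itself inflated.

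A second reply is that the size rests on an unknown. This stands too: at s of 0.2 to 0.3 the distortion is only +2% to +5%. Section 9.10 does provide for results off both ends of the assay range, which suggests widely spread values, but it says nothing direct about the within-child ratio.

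Third, the replacement is not free of judgement. Suppose a net 10% of children move from a below-limit value to 2 and the rest do not change. The geometric mean change is then 100 × ((2/c)^0.1 - 1), where c is the substitute: +15% for c = 0.5, +35% for 0.1 and +70% for 0.01. The substitute must therefore be stated and checked.

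Three stronger readings may tempt a reader, and the SAP supports none of them:
- *Fatty acids share the fault.* Section 9.8 does have them "summarised along with the change in FA and percentage change in FA at Day 10", but it names no mean or SD and leaves the displays to an external laboratory, and section 1.2 places that analysis outside this plan.
- *The comparison between arms loses power or gives a wrong inference.* No test or model of CRP or the cytokines is planned, so there is no power to lose.
- *The mean shows a rise when nothing at all has changed.* If no child changes, the mean is 0. The distortion needs children moving in both directions.

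**Conclusion.** The point holds for CRP and the cytokines, as a minor weakness in exploratory descriptive tables. The arithmetic mean of percentage change is biased upward as a summary of typical change and depends on spread. Under a normal log ratio centred at no change, the bias is negligible at log-SD 0.2, moderate at 0.5 (+13%) and large from about 0.8 upward (+38% or more). Which of these applies cannot be settled from the SAP. The consequence is that one row of a table may be misread, while the median and absolute change alongside remain sound.

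The zero created by the cytokine rule is a separate gap that needs no assumption about spread. It follows from the rule as written, for any analyte with a limit of 1, 0.1 or 0.01.

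**What to change.** In 9.9 and 9.10:
1. Replace the mean (SD) of percentage change with the geometric mean of the Day 10/Day 0 ratio and its 95% CI per arm. Calculate both from log values and back-transform; they may be shown as a percentage.
2. Keep the median, minimum and maximum, the absolute change and the CRP counts as they are.
3. For these tables, replace a '<x' result with a fixed positive value such as x/2, and repeat the summary with a second substitute, such as x/10, as a check. State how many values were substituted for each analyte at Day 0 and at Day 10.

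The cost is a few lines of SAP wording, a log transform and one repeat of the table. The downside is some dependence on the substitute where many values lie below the limit; the repeat with the second substitute shows how much.

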9.10. Pro-inflammatory cytokines

Pro-inflammatory cytokines (including IL-1ß, IL-2, IL-4, IL-5, IL-6, IL-7, IL-8, IL-10, IL-12p70, IL-13, IL-17, TNF- $\dot{\alpha}$, G-CSF, GM-CSF, IFN- γ , MCP-1 (MCAF) and MIP-1 β) will be summarised at Day 0 and 10 along with the change in pro-inflammatory cytokines and percentage change in pro-inflammatory cytokines at Day 10. The output will present the number of subjects, mean (with standard deviation) and median, minimum and maximum for each treatment group.

For laboratory values that are above or below the lower limit of quantification or out of range (OOR), that have character values starting with "<" or ">," numeric values will be derived using the following rules, where, for example, IL5I is the character result in standard units, and IL5 is the numeric version of the result:

if IL5I > x then IL5 = x + 1, where x is an integer ≥ 1 . if IL5I > x.y then IL5 = x.y + 0.1, where x, y are integers. if IL5I > x.yz then IL5 = x.yz + 0.01, where x, y, z are integers etc.

if IL5I "< x" then IL5 = x - 1, where x is an integer >= 1. if IL5I "< x.y" then IL5 = x.y - 0.1, where x, y are integers. if IL5I "< x.yz" then IL5 = x.yz - 0.01, where x, y, z are integers etc.

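### The cytokine rule for results below the limit gives a value set by how many decimals are printed, anywhere from 0 to almost the whole limit

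*SAP*

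**What the plan says.** SAP Section 9.10 covers laboratory results "that have character values starting with '<' or '>,' numeric values will be derived using the following rules". There are three branches in each direction, chosen by the number of decimals in the printed limit.

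- For '>' results: "then IL5 = x + 1, where x is an integer ≥ 1"; "then IL5 = x.y + 0.1, where x, y are integers"; "then IL5 = x.yz + 0.01, where x, y, z are integers etc".
- For '<' results the SAP gives the mirror image: the limit minus 1, minus 0.1 or minus 0.01. The integer branch allows a limit of 1. The decimal branches set no lower bound.

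These numbers feed the Day 0 and Day 10 summaries and "the change in pro-inflammatory cytokines and percentage change in pro-inflammatory cytokines at Day 10". The output for each is "number of subjects, mean (with standard deviation) and median, minimum and maximum for each treatment group". Section 7.1 defines change as "calculated by subtracting the baseline value from the post-baseline value" and sets it to missing only when one of the two values is missing.

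Section 1.2 lists change in pro-inflammatory cytokines at Day 10 among the secondary endpoints. Section 9.10 names 17 cytokines and plans no model or test for them. It does not plan to report how many results were below the limit.

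**The concern.** A result below the limit of quantification says only that the true value lies between 0 and the limit. Any substitution is arbitrary, but it should at least be the same fraction of the limit every time, so that a reader knows what was assumed. Here the assumption is set by typography. One analyte's undetectable results may be taken as zero and another's as practically the full limit, with nothing in the output to show which.

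Two further effects can follow. A substituted 0 is not a missing value, so it stays in the data and can become the denominator of a percentage change. And if the laboratory's number format were not constant across visits, the rule would create a change where none was measured. The SAP writes integer, one-decimal and two-decimal branches for the same example variable (IL5), so it allows for more than one format. It does not say that formats actually vary within an analyte.

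At stake is whether the means, SDs and percentage changes for a listed secondary endpoint can be interpreted.

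**Working it through.** The SAP states no figure of its own to reproduce, so the check applies its rule literally.

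**Inputs.** The '<' rule from Section 9.10; the definition of change from Section 7.1. Three assumptions: the example limits, a Day 10 value of 4 for illustration, and percentage change = 100 × (Day 10 − Day 0) / Day 0. The last is assumed because the formula in Section 7.1 is not legible in the available text.

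**Step 1: substituted value.** For a limit L printed with d decimals, value = L − 10^(−d), and its fraction of the limit is 1 − 10^(−d)/L.

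| Printed | Value | Fraction of limit |
|---|---|---|
| `<1` | 1 − 1 = 0 | 0% |
| `<1.0` | 1.0 − 0.1 = 0.9 | 90% |
| `<1.00` | 1.00 − 0.01 = 0.99 | 99% |
| `<2` | 2 − 1 = 1 | 50% |
| `<2.0` | 2.0 − 0.1 = 1.9 | 95% |
| `<2.00` | 2.00 − 0.01 = 1.99 | 99.5% |
| `<0.1` | 0.1 − 0.1 = 0 | 0% |
| `<0.10` | 0.10 − 0.01 = 0.09 | 90% |
| `<0.01` | 0.01 − 0.01 = 0 | 0% |
| `<2.31` | 2.31 − 0.01 = 2.30 | 99.6% |

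Rows with the same numeric limit show the dependence on format. Rows with different limits show how far the assumed fraction can vary between analytes even if each analyte has one constant format. Zero arises only when the limit is exactly one unit in its last printed place.

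**Step 2: change from an undetectable Day 0 value to a Day 10 value of 4 (assumed).**

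| Day 0 | Change | Percentage change |
|---|---|---|
| `<1` | 4 − 0 = 4 | 4/0, undefined |
| `<1.0` | 4 − 0.9 = 3.1 | 3.1/0.9 = +344.4% |
| `<1.00` | 4 − 0.99 = 3.01 | 3.01/0.99 = +304.0% |
| `<2` | 4 − 1 = 3 | 3/1 = +300% |
| `<2.0` | 4 − 1.9 = 2.1 | 2.1/1.9 = +110.5% |
| `<2.00` | 4 − 1.99 = 2.01 | 2.01/1.99 = +101.0% |

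Absolute change exists in every row. A substituted 0 on Day 10 rather than Day 0 causes no division problem; with a positive baseline it gives −100%.

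**Step 3: undetectable at both visits.** With the same printed limit at both, the change is exactly 0. With `<2` on Day 0 and `<2.0` on Day 10, it is 1.9 − 1 = +0.9, or +90%. With `<2` and `<2.00`, it is 1.99 − 1 = +0.99, or +99%.

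**Step 4: the '>' rule.** It depends on format in the same way but with little relative effect: `>1000` becomes 1001 and `>1000.00` becomes 1000.01.

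**Step 5: a fixed fraction.** With half the limit, `<2`, `<2.0` and `<2.00` all become 1, and the percentage change to 4 is +300% each time. `<1`, `<1.0` and `<1.00` all become 0.5, giving 3.5/0.5 = +700% each time. No zero can arise.

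**The case against.** The strongest reply is that the harms are conditional. The SAP gives no assay limits, no printed precision and no share of results below the limit. A zero needs a limit of exactly 1, 0.1, 0.01 and so on in its printed form, and nothing shows that any of the 17 analytes has one. A spurious change needs the format of one analyte to differ between visits, and nothing shows that either.

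The reach is also limited. The endpoint in Section 1.2 is change, not percentage change, and absolute change survives a zero baseline. Each substituted value is wrong by at most the limit itself. Medians are already planned. Cytokines do not appear in Table 1, Section 6 calls all analyses exploratory, the same rule applies in both arms, and the weight-gain analysis is untouched.

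All of that stands, and it bounds the point. A reader might infer that the changes will be corrupted, or that the children with low baselines will systematically drop out of the percentage change. The document supports neither: frequency is unknown, and loss would occur only for a Day 0 result whose limit is one unit in its last printed place. Any handling of a zero denominator attached to the illegible formula also cannot be excluded.

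The reply does not rescue the rule. It is fully specified, and it assigns fractions of the limit on no assay ground even when every analyte has one constant format.

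**Conclusion.** The point holds as a defect in a stated derivation. The value given to an undetectable cytokine depends on print precision and can lie anywhere from 0% to nearly 100% of the limit. This part follows from Section 9.10 alone.

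Two consequences are conditional: an undefined percentage change (needs a Day 0 zero and division by baseline) and a spurious change between two undetectable results (needs formats that differ between visits). Their frequency cannot be estimated from the SAP.

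The effect is confined to descriptive summaries of one exploratory secondary endpoint. Means, SDs and percentage changes are the exposed figures; medians are less so. The correction is worth making because the rule is arbitrary and easily replaced, not because it threatens the trial's main conclusion.

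**What to change.** In Section 9.10, replace the '<' rule by one fixed positive fraction of the numeric limit for each analyte, for example half the lower limit of quantification. Apply it identically at Day 0 and Day 10 and in both arms, however the limit is printed. If the laboratory reports more than one limit for an analyte, state which one is used. Add to the cytokine table the number and percentage of results below the limit by arm and visit, and rely on medians where that share is large.

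Changing the '>' rule, or summarising change as a ratio of geometric means, is optional; neither is needed to cure the defect.

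The cost is a few lines of SAP wording, a changed derivation step and one added row per analyte in the output. No new data are needed. The downside is that half the limit is still a substitution, which is why the counts should stand beside it.
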